2.2. Study Objectives

2.2.1. Primary Immunogenicity Objectives

- *To describe the immune response as measured by hSBA performed with 4 primary MnB strains, 2 expressing an LP2086 subfamily A protein and 2 expressing an LP2086 subfamily B protein, measured 1 month after the third vaccination with bivalent rLP2086, in healthy toddlers aged 12 to <18 months at study entry.*
- *To describe the immune response as measured by hSBA performed with 4 primary MnB strains, 2 expressing an LP2086 subfamily A protein and 2 expressing an LP2086 subfamily B protein, measured 1 month after the third vaccination with bivalent rLP2086, in healthy toddlers aged 18 to <24 months at study entry.*

2.2.2. Primary Safety Objective

- *To evaluate the safety profile of bivalent rLP2086 compared to a control (hepatitis A virus [HAV] vaccine), as measured by local reactions, systemic events, adverse events (AEs), serious adverse events (SAEs), newly diagnosed chronic medical conditions, medically attended events, and immediate AEs in healthy toddlers 12 to <18 months and 18 to <24 months of age at study entry, and in both age strata combined.*

2.2.3. Secondary Immunogenicity Objectives

- *To describe the immune response as measured by hSBA performed with 4 primary MnB test strains, 2 expressing an LP2086 subfamily A protein and 2 expressing an LP2086 subfamily B protein, measured 1 month after the third vaccination with bivalent rLP2086, in healthy toddlers aged 12 to <24 months at study entry (ie, both age strata combined).*
- *To describe the immune response as measured by hSBA performed with 4 primary MnB test strains, 2 expressing an LP2086 subfamily A protein and 2 expressing an LP2086 subfamily B protein, measured 1 month after the second vaccination, and 6, 12, 24, 36, and 48 months after the third vaccination in healthy toddlers aged 12 to <18 months and 18 to <24 months at study entry, and in both age strata combined.*

2.2.4. CCI [REDACTED]

- CCI [REDACTED]
- CCI [REDACTED]

3. INTERIM ANALYSES, FINAL ANALYSES AND UNBLINDING

3.1. Blinding

As the physical appearances of bivalent rLP2086, HAV vaccine, and saline differ, dispensing and administration of the investigational product will be performed by an unblinded dispenser/administrator. The unblinded dispenser/administrator will at all times (other than as described in Section 5.2.2 of the protocol keep the identity of the randomized, allocated vaccination concealed from parent(s)/legal guardian/other family members and blinded study staff. Unblinded study staff will not take part in any subject assessments/interviews/data collection or CRF data entry; however, investigational product dispensing and administration should be noted in the study/medical record (while maintaining the blind) and accountability logs.

So that subject safety and stopping rule criteria can be closely monitored and responded to in a timely fashion, a subset of sponsor representatives will be unblinded (see the IRC charter). These include the medical clinicians, clinical scientists, and statisticians. In addition, an investigational product monitor(s) will be required to monitor the pharmacy dispensing records.

3.1.1. Blinded Study Personnel

All other site personnel, including the investigator, investigator staff, subjects, and subjects' parent(s)/legal guardian, will be blinded to investigational product assignments until randomization allocations are made available.- Pfizer will release unblinding information to the investigator when all subjects have completed Visit 8 and before subjects reach Visit 10. Subjects will receive their randomization allocation at Visit 10. Additional information is included in the SRM (Study Reference Manual).

Stage 2 will be unblinded.

All immunogenicity assays will be performed in a central laboratory by blinded laboratory staff.

3.1.2. DMC Reports

As this study is utilizing E-DMC, the unblinded randomization codes will be released to an Independent Statistical Center (ISC) prior to the DMC meeting. The ISC is not a part of the sponsor's organization and is a statistical team not involved in the conduct of the study. ISC will be producing unblinded data summary reports on safety data and deliver the safety reports to the DMC members through a secure portal independent of the Sponsor.

3.1.3. Assay Testing Allocation

The study design designates randomization of sera from individual study subjects for initial testing with 2 of the 4 primary hSBA test strains. At a minimum, approximately 50% of subjects from each age group will be randomly selected to test for hSBA on strains CCI (A22) and CCI (B24), and the other 50% of subjects from each age group will be tested for hSBA on strains CCI (A56) and CCI (B44). Serum bactericidal assay (SBA) with all 4 primary MnB test strains may be performed with individual serum specimens when the volume of the sample permits. The independent statistical center (ISC, a statistical team not involved in the conduct of the study) will provide the subject list to test hSBA on the 2 strains to the Sponsor's sample management team without the group assignment. The hSBA testing personnel will be blinded to the subject group allocation.

3.2. Primary Analysis

The primary analysis will be performed when all of the immunogenicity data through Visit 7 and all the safety data up to and including Visit 8 are available. The final analysis will include all data not reported in the first CSR and will be performed separately after all of the subjects finish the study when all of the data are available. As this study is not a hypothesis-testing study, no alpha will be adjusted on these analyses.

Interim summaries of immunogenicity and safety data may be generated to summarize key immunogenicity and safety endpoints. As this study is not a hypothesis-testing study, no alpha will be adjusted on these analyses.

3.3. Safety Analysis

The safety data will be reviewed on an ongoing basis, and no alpha will be adjusted for these multiple looks at the safety data.

3.3.1. Internal Review and Data Monitoring Committees

This study will use both an unblinded IRC and an unblinded EDMC. See Section 9.4 of the protocol for detailed responsibilities for both IRC and EDMC.

4. HYPOTHESES AND DECISION RULES

4.1. Statistical Hypotheses

There are no statistical hypotheses specified in the protocol. All safety and immunogenicity analyses will be descriptively summarized.

4.2. Statistical Decision Rules

Not applicable.

5. ANALYSIS SETS

5.1. Full Analysis Set

An intent-to-treat (ITT) population will be defined that includes all subjects who are randomized.

5.2. ‘Per Protocol’ Analysis Set

The ‘Per Protocol’ Analysis Set will be used for the immunogenicity analysis. It will be named as Evaluable Immunogenicity Population. The evaluable immunogenicity population will be defined as described below.

This population is the primary population for immunogenicity analyses and includes subjects who:

1. Are eligible for the study (through 1 month post vaccination 3).
2. Have been randomized to a study group.
3. Have received scheduled investigational products as randomized.
4. Have prevaccination blood drawn prior to the first vaccination dose and have post-vaccination 3 blood draw (Visit 7) within 28-42 days from the third vaccination (Visit 6).
5. Have a valid and determinate assay result for the proposed analysis.
6. Have received no prohibited vaccines or treatment.
7. Have no other major protocol violations as determined by the sponsor’s global medical monitor.

For above listed items, 1 through 5 will be computerized checks of the data, while items 6 and 7 will be determined by clinical review. A major protocol violation is a protocol violation that, in the opinion of the sponsor's global medical monitor would materially affect assessment of immunogenicity, eg, subject receipt of a prohibited vaccine or medication that might affect immune response or a medication error with suspected decrease in potency of the vaccine. The sponsor's global medical monitor will identify those subjects with protocol violations before any immunogenicity analysis is carried out.

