9.1.5. Immunogenicity Analysis Populations

An evaluable immunogenicity population and a modified intent-to-treat (mITT) population will also be defined for the immunogenicity analyses. The evaluable immunogenicity population will be the primary population for the immunogenicity analyses. For the immunogenicity analysis, subjects will be analyzed according to the investigational product to which they were randomly assigned.

In general, the evaluable population will include all subjects who were randomly assigned to the study group of interest, were eligible, received all investigational products as randomized, had blood drawn for assay testing within the required time frames, had valid and determinate assay results for the proposed analysis, and had no major protocol deviations. A major

B1971035

Final Protocol Amendment 2, 19 April 2016

protocol deviation is one that, in the opinion of the sponsor's global medical monitor, would materially affect assessment of immunogenicity, eg, subject receipt of a prohibited vaccine or medication that might affect immune response or a medication error with suspected decrease in potency of the vaccine.

The mITT population will include all randomly assigned subjects who have at least 1 valid and determinate assay result.

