8.2.2. Analysis of Secondary Endpoints

All of the analyses mentioned in [Section 8.2.1](#) to be performed on the mITT population are considered as secondary analyses.

Secondary analyses also will include percent of subjects with hSBA titers \geq LLOQ for each of the primary 4 MnB test strains 1 month following the third vaccination for both the evaluable immunogenicity population and for the mITT population.

The percentage of subjects with hSBA titers \geq LLOQ for each of the primary 4 MnB test strains 1 month following the second vaccination, and at 6, 12, 24, 36, and 48 months after the third vaccination will be analyzed using both the evaluable immunogenicity population and the mITT population.

The percentage of subjects with hSBA titers \geq LLOQ, 1:4, 1:8, 1:16, 1:32, 1:64, 1:128 for each of the 4 primary MnB test strains at each applicable blood sampling visit will be analyzed using both the evaluable immunogenicity population and the mITT population.

The GMTs for each of the primary MnB test strains at each applicable blood sampling visit will be summarized for the evaluable immunogenicity population and the mITT population.

The empirical reverse cumulative distribution curves (RCDCs) will be presented graphically for each of the 4 primary MnB test strains, each group, and each sampling time point.

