8.2.6. Analyses of Study Conduct

8.2.6.1. Subject Disposition, Vaccination Administration, Blood Samples

The number and percentage of subjects who are randomized, take each dose of investigational product, withdrew during the vaccination phase, completed the vaccination phase, completed and withdrew in the follow-up phase in stage 1, entered stage 2 and completed stage 2, and are major protocol violators and are major protocol violators (excluded from evaluable immunogenicity population at 1 month following vaccination 3), will be summarized. The reasons for withdrawal will also be tabulated.

In addition, the relationship of randomized vaccine group to actual vaccine received will be presented as a cross tabulation of the actual sequence received versus the randomized vaccine administration regimen.

For each blood draw, the number and percentage of subjects randomized, vaccinated (visits 1, 4, 6), and providing blood samples within the protocol-specified time frame, as well as before and after the specified time frame, will be tabulated.

Similarly, for each vaccination visit, the number and percentage of subjects who are enrolled, vaccinated (visits 1, 4, 6), and vaccinated within the protocol-specified time frame, before and after the specified time frame will be tabulated.

The number and percentage of subjects included in each analysis population will be summarized.

The ITT population will be used to generate these tables. All of the summary tables will be presented for each randomized group and total population.

A listing of subjects' non-compliant vaccine administration will be provided. The protocol violators will also be listed. Subjects receive the vaccine not as randomized will be listed as well. A listing of subjects that withdrew and subjects who withdrew due to AEs will be provided.

Listings for the subjects with flags to be included or excluded in each analysis population will be provided. The reason for not including a subject in a specific analysis population will be listed.

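### The evaluable population in SAP 5.2 has a post-vaccination draw window for Visit 7 only, yet SAP 8.2.2 uses it for every sampling visit

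*SAP*

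**What the plan says.** SAP 5.2 names the evaluable set as the primary population for immunogenicity. The criteria that matter here are:

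- Item 1: "Are eligible for the study (through 1 month post vaccination 3").
- Item 3: "Have received scheduled investigational products as randomized".
- Item 4: a baseline draw before dose 1, and subjects must "have post-vaccination 3 blood draw (Visit 7) within 28-42 days from the third vaccination (Visit 6").
- Item 5: "Have a valid and determinate assay result for the proposed analysis".
- Items 6 and 7: no prohibited vaccine or treatment, and no other major violation as judged by the medical monitor.

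Items 1 to 5 are programmed checks; items 6 and 7 are clinical review.

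SAP 8.2.2 then applies this set, alongside mITT, beyond Month 7. The proportions at or above LLOQ "1 month following the second vaccination, and at 6, 12, 24, 36, and 48 months after the third vaccination will be analyzed using both" populations, and the GMTs "at each applicable blood sampling visit will be summarized for the evaluable immunogenicity population and the mITT population".

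Protocol 9.1.5 describes the evaluable population more broadly. In general, it covers subjects who "had blood drawn for assay testing within the required time frames", with no restriction to Visit 7. SAP 8.2.6.1 reports the numbers of subjects "providing blood samples within the protocol-specified time frame, as well as before and after the specified time frame, will be tabulated", but does not link that table to exclusion from any population.

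**The concern.** A per-protocol immunogenicity table should contain samples drawn at the time its label states. SAP 5.2 secures that for Visit 7 alone. Item 5 adapts to the analysis, but it concerns assay validity and not the date of the draw.

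Two consequences follow from the text:

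- **(a) Mistimed samples are kept.** Samples outside the protocol windows at Visits 5, 8, 9 and 11-13 meet items 1 to 5. Only a case-by-case decision under items 6-7 and SAP 5.6.2 would remove them.
- **(b) Well-timed samples are dropped.** A child who received all three doses and gave a valid, in-window Visit 5 sample leaves the post-dose-2 table if the Visit 7 draw, months later, is missed or falls outside 28-42 days.

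At stake is what the secondary tables mean. The post-dose-2 and persistence results would mix in-window and out-of-window samples, and the post-dose-2 result would be conditional on a later attendance that has no bearing on the response to dose 2.

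**Working it through.** **Windows against criteria.** The windows are from the Schedule of Activities and protocol 6.1 and 6.2.

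| Draw | Protocol window | Timing check in SAP 5.2 |
|---|---|---|
| Visit 5 | 28-42 days after Visit 4 | none |
| Visit 7 | 28-42 days after Visit 6 | item 4 |
| Visit 8 | 168-196 days after Visit 6 | none |
| Visit 9 | 337-365 days after Visit 6 | none |
| Visits 11, 12, 13 | 24, 36, 48 months after dose 3, ±30 days | none |

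Six of the seven post-baseline draws have a protocol window but no timing criterion.

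**How late a sample could be.** Visit 6 is due 105-126 days after Visit 4. A Visit 5 draw taken just before Visit 6 would be 105 − 42 = 63 to 126 − 42 = 84 days past its window and would still meet items 1 to 5. In Stage 2, protocol 5.7.4 delays draws for 6 months after blood products or immunoglobulin, which can exceed ±30 days.

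**The plan's own figure.** Protocol 9.1 assumes 20% nonevaluable: 110 × 0.8 = 88 and 220 × 0.8 = 176. With a null rate of 50%, a true rate of 65% and 0.025 one-sided, the exact test gives 79.7% power at n = 88 (reject at 54 or more) and 97.8% at n = 176 (reject at 102 or more). This reproduces the stated figures of about 80% and 98%. The present point does not depend on them.

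**Numbers per age stratum at the selected dose.** Sentinel 33 × 2/3 = 22, plus expanded 132 × 2/3 = 88, gives 110. At the minimum strain-pair allocation, each strain is tested in 110/2 = 55, of whom 55 × 0.8 = 44 are evaluable and 11 are not. If all four strains are tested, the figures are 110, 88 and 22.

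**Outer limit for (b).** If the whole 20% allowance came from missed or mistimed Visit 7 draws in children with valid Visit 5 samples, 11 of 55 (or 22 of 110) would be lost. Clopper-Pearson 95% intervals near a 50% rate:

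| Set | Interval | Half-width, points |
|---|---|---|
| 22/44 | 34.6-65.4% | 15.4 |
| 28/55 | 37.1-64.6% | 13.8 |
| 44/88 | 39.1-60.9% | 10.9 |
| 55/110 | 40.3-59.7% | 9.7 |

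If x omitted children respond d points differently from the 44 kept, the estimate shifts by d·x/(44 + x):

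- x = 0: 0
- x = 5, d = 10: 1.0 point
- x = 11, d = 10: 2.0 points
- x = 11, d = 20: 4.0 points

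With 88 kept and x = 22, the results for d = 10 and d = 20 are the same. The values of d are assumptions.

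**Illustration for (a).** One sample is worth at most 1/44 = 2.3 points or 1/88 = 1.1 points. If a fraction f of the analysed samples is out of window and responds d points differently, the shift is f·d: 0.05 × 10 = 0.5; 0.10 × 20 = 2.0; 0.15 × 20 = 3.0 points. Both f and d are assumptions.

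**The case against.** The strongest reply is that the set is meant as a fixed Month 7 cohort. SAP 8.2.6.1 refers to the evaluable population at 1 month after vaccination 3, and the SAP 2.0 change log says the definition was aligned with other MnB protocols. A fixed cohort is a legitimate choice for persistence. However, the SAP does not say that it intends one, and a fixed cohort would still admit mistimed samples at later visits, so (a) remains.

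Four further objections narrow the point:

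- **Missed dose 3.** A reader might infer that dropping a child who missed dose 3 from the post-dose-2 table also departs from the protocol. It does not: protocol 9.1.5 itself requires receipt of all products as randomised. Only the Visit 7 draw requirement is at issue.
- **No exclusion possible.** A reader might infer that nothing can remove a mistimed sample. Item 7 and SAP 5.6.2 allow the medical monitor to exclude major deviations, at the final analysis as well as the primary. This is real but discretionary, and it is not a window.
- **Windowing specifications.** SAP 2 says these are prepared separately, and they were not available. They may already settle (a). What can be said is that SAP 5.2 neither states nor cites such a rule. Point (b) follows from item 4 itself.
- **Size.** The 20% allowance covers every cause of nonevaluability, including ineligibility, early dropout and insufficient or indeterminate sera. Much of that would remove a Visit 5 result under any definition, so 11 of 55 is an outer limit and not an estimate.

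**Conclusion.** The point holds as a gap in the SAP's definition. No stated timing rule covers six of the seven post-baseline draws, which is narrower than protocol 9.1.5, and the Visit 7 requirement removes some valid post-dose-2 samples without need.

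The consequence is limited. A reader might infer that the primary analysis is compromised. It is not, because item 4 gives the Month 7 endpoint its correct window. The affected tables are secondary and descriptive, the study tests no hypotheses, mITT tables are planned for the same endpoints, and out-of-window draws are at least counted.

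The size cannot be computed, because the documents give no out-of-window rate. Under the assumptions shown, the shifts are 0 to 4.0 points for (b), with 4.0 at the outer limit, and 0.5 to 3.0 points for (a). Their direction is not predictable. All are small beside half-widths of 9.7 to 15.4 points. The SAP should be corrected, but the trial's main result does not depend on it.

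**What to change.** Keep the current set for the Visit 7 primary endpoint. In SAP 5.2:

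1. For every other visit's evaluable table, require that the sample analysed was drawn within that visit's protocol window. If the windowing specifications already say this, cite them instead.
2. For the post-dose-2 table, replace the Visit 7 draw requirement with the Visit 5 window (28-42 days after Visit 4). Leave the dosing criterion as it is.
3. Keep and flag Stage 2 draws delayed under protocol 4.4 or 5.7.4, since those delays follow the protocol.
4. If a fixed Month 7 cohort is intended for persistence, say so, and still apply each visit's window.

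The cost is SAP wording and visit flags built from draw and vaccination dates that SAP 8.2.6.1 already needs. The downside is that denominators will differ by visit, and a few samples will move into or out of the evaluable tables.

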5.3. Safety Analysis Set

The safety population will be used for all safety analyses. The safety population will include all subjects who have received at least 1 dose of an investigational product (bivalent rLP2086 or control) and for whom safety data are available. For the safety analysis, subjects will be analyzed according to the investigational product received.

Separate safety populations will be defined for each vaccination visit: vaccination visit 1, vaccination visit 2, vaccination visit 3, and follow-up phase for stage 1.

1. Vaccination 1 Safety Population: This population will include all subjects who received the first dose of investigational product (bivalent rLP2086 or HAV) at visit 1, and for whom safety information from visit 1 to prior to visit 4 is available.
2. Vaccination 2 Safety Population: This population will include all subjects who received the investigational product (bivalent rLP2086 or saline) at visit 4, and for whom safety information from visit 4 to prior to visit 6 is available.
3. Vaccination 3 Safety Population: This population will include all subjects who received the investigational product (bivalent rLP2086 or HAV) at visit 6, and for whom safety information from visit 6 up to visit 7 is available.
4. Follow-up Safety Population for Stage 1: This population will include all subjects who received at least 1 dose of investigational product (rLP2086 or HAV vaccine or saline) and for whom safety information is available from after visit 7 to up to visit 8. Subjects who receive the wrong investigational product and are followed for 6-month safety will not be included in this population.

5.4. Other Analysis Sets

All randomized subjects who have at least 1 valid and determinate assay result related to a proposed analysis will be included in the modified intent-to-treat (mITT) population. This analysis set is for the immunogenicity analysis.

5.5. Treatment Misallocations

- Randomized but not vaccinated: These subjects will be included in the ITT population and excluded from any safety analyses. They might be included in the mITT population if any assay results are available and will be reported under their randomized group for immunogenicity analyses.

- Vaccinated but not randomized: by definition they will be excluded from the immunogenicity analyses since randomized group is missing, but will be reported under the vaccine group they actually received for all safety analyses.
- Randomized but received incorrect vaccine: They will be included in the mITT population if any assay results are available and will be reported under their randomized group for immunogenicity analyses, but may be reported under the group they actually received for some safety analyses (eg, safety data at each dose can be summarized, but safety data at any dose or follow-up can't be summarized as no group can be assigned). All of the safety data will be listed for subjects who did not take the correct vaccine as randomized.

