9.2. Safety Analysis

Similar to the immunogenicity analysis, the control group and each dose-level group from different cohorts within the same age stratum will be pooled for analysis. All of the safety analyses will be summarized for each age stratum separately as well as for the overall populations. Subgroup analyses on primary safety endpoints will also be performed by race and sex. Additionally, race and sex subgroup analyses will be performed within age/dose level.

The safety population will be used for all safety analyses. The safety population will include all subjects who have received at least 1 dose of an investigational product and for whom safety data available. For the safety analysis, subjects will be analyzed according to the investigational product received.

The proportion of subjects reporting local reactions at the investigational product administration sites, systemic events and the use of antipyretics within the 7-day period after each vaccination will be descriptively summarized by group. Severities of local reactions and systemic events reported after each vaccination will also be descriptively summarized by group. Two (2)-sided 95% CIs based on the Clopper-Pearson method²² will be presented with the proportions.

All of the AEs and SAEs will be categorized according to Medical Dictionary for Regulatory Activities (MedDRA) and will be summarized by group. A medically attended event is defined as a nonserious AE that results in an evaluation at a medical facility. A newly diagnosed chronic medical condition is defined as a disease or medical condition not previously identified that is expected to be persistent or otherwise long-lasting in its effects. All summaries will show the number and percentage of subjects experiencing at least 1 event and the number of events. Two (2)-sided 95% CIs based on the Clopper-Pearson method will also be presented for the AE and SAE percentages.

Comparisons will be made on the safety endpoints between bivalent rLP2086 and the control. The reactogenicity data (including use of antipyretic medication) and immediate AEs between the vaccine and control will be compared with an unconditional exact test.²³ The Fisher exact test will be used to compare the endpoints related to AEs, SAE, MAEs, and NDCMCs

B1971035

Final Protocol Amendment 2, 19 April 2016

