10.1.5.4.1. Analyses Impacted

There are 5 safety populations defined: Safety Population; Vaccination 1 Safety Population; Vaccination 2 Safety Population; Vaccination 3 Safety Population, and Follow-up Safety Population for Stage 1. The analysis on the CRF related safety summary will use the corresponding safety population listed in [Table 12](#) as the population definition is the same as the denominator minus the numerator, except for the analysis interval of ‘During the AE collection period’.

The primary analysis on SAE, medically attended AE, newly diagnosed medical condition ‘During the AE collection period’ will use the overall ‘safety population’ because this will capture any events that were reported during the study stay regardless study/vaccination phase completion status.

Additional analysis will be performed on the follow-up safety population for stage 1 for the endpoints of SAE, medically attended AE, newly diagnosed medical condition during the AE collection period, so that the estimation are based on subjects with complete safety information.

Supplementary analyses may be performed on ‘SAEs during the AE collection period’ among subjects who completed the study; ‘(S)AE during the vaccination phase’ among subjects who completed the vaccination phase.

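### SAP 5.3 and 5.5 take children given an incorrect vaccine out of the follow-up and any-dose safety percentages, against Protocol 9.2 and other parts of the SAP

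*SAP*

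**What the plan says.** Protocol 9.2 defines the population broadly: "The safety population will include all subjects who have received at least 1 dose of an investigational product", provided safety data exist. It then fixes the grouping: "For the safety analysis, subjects will be analyzed according to the investigational product received". It makes no exception for dosing errors.

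SAP 5.3 repeats that definition, but ends its description of the Stage 1 follow-up population with: "Subjects who receive the wrong investigational product and are followed for 6-month safety will not be included in this population".

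SAP 5.5 covers the randomized child who received an incorrect vaccine. Such a child "may be reported under the group they actually received for some safety analyses (eg, safety data at each dose can be summarized", whereas "safety data at any dose or follow-up can't be summarized as no group can be assigned". It adds: "All of the safety data will be listed for subjects who did not take the correct vaccine as randomized". A child vaccinated without being randomized is treated differently: excluded from immunogenicity analyses, "but will be reported under the vaccine group they actually received for all safety analyses".

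Other parts of the SAP keep every vaccinated child. Table 8 gives the any-vaccination, vaccination-phase and Visit 1 to Visit 8 intervals to the overall safety population. Section 10.1.5.3 says that this population should contain any vaccinated subject. Section 10.1.5.4.1 chooses it for SAEs, MAEs and NDCMCs over the whole collection period because "this will capture any events that were reported during the study stay regardless study/vaccination phase completion status".

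**The concern.** The primary safety endpoints for SAEs, MAEs and NDCMCs use five kinds of interval: 30 days after each vaccination, 30 days after any vaccination, the vaccination phase, the follow-up phase, and the whole collection period. Only the first looks at one dose at a time. A rule that removes misdosed children from cross-dose summaries is a post-randomization exclusion of exposed children from primary safety percentages, on a criterion tied to unintended exposure.

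The stated reason is that no group can be assigned. That is a fair description of a truly mixed series when no rule exists, but 5.5 applies it more widely. A child given the same wrong product at every visit has an obvious group. The control regimen is itself a mixed series (HAV vaccine, saline, HAV vaccine), so a control child given HAV vaccine in place of saline has still received only control products. Neither case is exempted.

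The wording of 5.5 is also permissive (*may*, *eg*). Sponsor clinicians and statisticians are unblinded (Protocol 5.2.1.1), so a placement left open could be settled by people who know both the group and the outcome.

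**Working it through.** **1. The rule for each interval**

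| Interval (SAP Table 8) | Population in Table 8 | Effect of SAP 5.3 / 5.5 on a misdosed child |
|---|---|---|
| 1–3: 30 days after each vaccination | Per-vaccination safety | Can be counted, by product received |
| 4: 30 days after any vaccination | Safety | 5.5 says any-dose data cannot be summarized |
| 5: vaccination phase | Safety | Not named in 5.5, but it spans doses, so the same reasoning reaches it |
| 6: follow-up phase | Follow-up Stage 1 | Excluded in both 5.3 and 5.5 |
| 7: Visit 1 to Visit 8 | Safety | Not named in 5.5, but it spans doses; 10.1.5.4.1 says capture all events |

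For interval 6, Table 12 takes as denominator all children who received any vaccination and as numerator those with no adverse-event discussion recorded after Visit 7 up to Visit 8. Section 10.1.5.4.1 says that the population equals denominator minus numerator. A misdosed child with complete follow-up is therefore in under Table 12 and out under 5.3. Both cannot be programmed.

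**2. How much of the collection period the per-dose windows cover**

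Inputs are the visit windows in the Schedule of Activities: Vaccination 1 to 2, 42–70 days; Vaccination 2 to 3, 105–126 days; Vaccination 3 to Visit 8, 168–196 days. Table 8 runs each per-dose window from the vaccination date to that date + 30, both inclusive, which is 31 days.

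- Visit 1 to Visit 8, counted inclusively: shortest 42 + 105 + 168 + 1 = 316 days; longest 70 + 126 + 196 + 1 = 393 days.
- Per-dose windows: 3 × 31 = 93 days. They do not overlap, since doses are at least 42 days apart.
- Covered: 93/393 = 24% to 93/316 = 29%. Outside: 71% to 76%.

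This assumes three doses given within the scheduled windows.

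**3. Size of the effect on a percentage**

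The plan gives no figure on this point and no rate of dosing errors. Group sizes follow from Protocol 3.2: each sentinel cohort of 33 at 2:1 gives 22 + 11, and expanded enrollment of 132 per age stratum at 2:1 gives 88 + 44. Per stratum, the selected dose has 22 + 88 = 110, which matches the 110 in Protocol 9.1. The non-selected dose has 22 and control has 11 + 11 + 44 = 66. With the same dose selected in both strata, the combined group is 220.

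Assume one misdosed child who has the only event in the group. The intervals are exact (Clopper-Pearson), as in SAP 8.1.2; for zero events the upper limit reduces to 1 − 0.025^(1/n).

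| Group | Child kept | Child dropped |
|---|---|---|
| Non-selected dose, one stratum | 1/22 = 4.5% (0.1% to 22.8%) | 0/21 (upper limit 16.1%) |
| Control, one stratum | 1/66 = 1.5% (upper limit 8.2%) | 0/65 (upper limit 5.5%) |
| Selected dose, one stratum | 1/110 = 0.9% (upper limit 5.0%) | 0/109 (upper limit 3.3%) |
| Selected dose, strata combined | 1/220 = 0.45% (upper limit 2.5%) | 0/219 (upper limit 1.7%) |

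**The case against.** A reader might infer that events after a dosing error are left out of the primary safety percentages altogether, or lost. The documents do not support that. The 30 days after each vaccination are themselves a primary interval, and so are the per-vaccination reactogenicity and immediate-AE endpoints; 5.5 lets these children be counted there by product received. All their safety data are listed, SAP 8.2.5.2.1 lists every SAE with causality and timing relative to vaccination, SAP 8.2.6.1 cross-tabulates actual against randomized regimen, and medication errors have their own CRF (Protocol 8.4.1). The IRC and EDMC also review unblinded safety data.

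Nor do the documents establish that these children are removed from the whole-period analysis. Section 5.5 names only any-dose and follow-up data, as an example, while Table 8 and 10.1.5.4.1 point the other way. No passage says which prevails.

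It is tempting to state as fact that a wrong dose level triggers the rule. The SAP speaks only of an incorrect vaccine or wrong investigational product, and Protocol 8.4.1 lists incorrect product and incorrect dosage as separate errors. Because SAP 8.1.2.2 compares groups by dose, including a wrong dose level is a plausible reading, but it remains a reading.

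Two further points stand. Recording what was given at each visit does not by itself place a mixed series in one group, and Protocol 9.2 has no rule for that case. Errors may also be few, given IRT allocation with unique kit numbers, and the safety comparisons are descriptive, so no decision rule turns on them. These points limit the size of the problem. They do not remove the written follow-up exclusion or the contradiction between sections.

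**Conclusion.** The point holds as a conflict to be resolved. The follow-up exclusion is unambiguous in SAP 5.3 and 5.5 and departs from Protocol 9.2 and from the SAP's own Table 12. For the any-vaccination, vaccination-phase and Visit 1 to Visit 8 intervals, the SAP contradicts itself.

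If 5.5 is applied to all cross-dose intervals, a misdosed child's SAE, MAE or NDCMC is absent from every group percentage whenever it falls outside the per-dose windows, which is 71% to 76% of the collection period under the scheduled visit windows. If Table 8 prevails instead, such an event still counts in the whole-period percentage and is missing only from the follow-up one.

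The effect in practice cannot be sized, because the number of dosing errors is not given. The 1/22 and 1/110 examples show sensitivity to one child and are not forecasts; at 220 the shift is 0.45 percentage points. The rule is worth settling because it concerns primary safety endpoints and should be fixed before anyone chooses a placement with the results in view.

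**What to change.** - Delete the last sentence of the follow-up population definition in SAP 5.3.
- In SAP 5.5, replace the clause saying that the data cannot be summarized with one analysis-group rule for all cross-dose intervals (any vaccination, vaccination phase, follow-up, Visit 1 to Visit 8). A child given one consistent product goes under that product. A mixed series goes under the highest rLP2086 dose level received, with control only if no rLP2086 was received. A separate mixed-series column is an acceptable alternative; what matters is that one convention is prespecified.
- State whether a wrong dose level counts as an incorrect vaccine.
- Keep the per-vaccination summaries by product given at that visit.
- Keep the listing, footnote these children in the tables, and show the cross-dose results with and without them.
- Check that SAP 5.3, 5.5, Table 8, 10.1.5.3, Table 12 and 10.1.5.4.1 then agree with Protocol 9.2.

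The cost is SAP wording and a programming flag. The downside is small: under the highest-dose convention, an event that began before the wrong dose may be counted under a product not yet received. The footnote and the with-and-without comparison make that visible.
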